7.2.4 Conditioning Phase Check-in Visit (Day 14 ± 7 days) - Remote

Participants will take part in a remote visit via Zoom to report their ECIG use and cigarettes per day (CPD) (collected in the daily logs). Participants will complete the measures outlined in Table 1. Participants will complete an adverse events assessment and discuss challenges to using their e-cig daily and study staff will assist in problem solving barriers to compliance. At the end of the visit participants will be instructed to remain abstinent from all tobacco products including their ECIG for 14 hours prior to the next study visit and to eat before their next study visit.

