7.2.5 Post-Conditioning fMRI Visit (Day 28 ± 7 days) – In Person/Remote

Participants will attend a final visit to complete biomeasures, computerized surveys, the adverse events assessment, and the same fMRI tasks as the baseline MRI visit as indicated in Table 1. Some of the measures can be done remotely via Zoom, others will need to be completed in person. The remote assessments will be conducted via a Zoom session ± 3 days of the scheduled in-Person MRI. This is being done to limit the amount of face-to-face time during study visits. eCO will be measured and urine will be collected for cotinine and pregnancy tests. At the end of the visit, participants will be debriefed and counseled on smoking cessation. All participants will be given a copy of the Surgeon General's booklet 'How Tobacco Smoke Causes Disease' (SEE ATTACHMENT: Surgeon General's Booklet).

Table 1: Measures Table (Black X – In Person; Green X – Remote)

	Final Screening	Randomization/ Pre-Conditioning fMRI	Check-In	Post- Randomization fMRI
Visit	1	2	3	4
Day	-7	0	14	28
QUESTIONNAIRES				
Visit Screener	X			
Tobacco Use History	X			
Name Registry	X			
MRI Safety Form	X	X		X
Demographics	X			
Medical History	X			
Concomitant Medications	X	X	X	X
Adverse Event Assessment		X	X	X
Cigarette Details	X			
CCQ (Clinical COPD Questionnaire)	X	X	X	x
Alcohol Audit-C	X			
NIDA Quick Screen	X			
Environmental Smoke Questionnaire	X			
MINI Psychiatric Interview	X			
Daily Smoking and ECIG Use Logs	X (cigarette only)	X	X	X
Cigarette Dependence (Fagerstrom and Penn State Cigarette Dependence Index)		X	X	X
Minnesota Withdrawal Scale		X	X	X
Craving		X	X	X
Cigarette liking scale		X	X	X
ECIG Use History	X	X	X	X
ECIG evaluation scale			X	X
ECIG Side Effects			X	X
ECIG dependence			X	X
ECIG Perceived Health Risk			X	X
ECIP Patterns of Use			X	X
Perceived Benefits and Harms of Using ECIG		X		X
PROCEDURES				
B-SIT Smell Test		X		
fMRI Cue-Reactivity Task in Scanner		X		X
BIOMEASURES				
Pregnancy Test		X		X
Exhaled CO		X		X
Urine Sample Collection		X		X
NICCHECK Rapid Cotinine Test		X		X

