7.3 Duration of Participation

All participants will be in the study for a period of at least 5 weeks but no more than 8 weeks and will attend 2 in-person clinic visits at the study center. The randomization/pre-conditioning visit (Visit 2), remote check in (Visit 3) and post-conditioning visit (Visit 4), will happen within a 4 week period.

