Aim 2: Examine the effect of flavor and nicotine on ECIG odor cue-reactivity after conditioning. Two-sample t-test will be conducted in FSL for the strawberry vanilla>rose and tobacco>rose odor difference score z- statistic images comparing the 18 mg to 0mg nicotine content ECIG groups. A paired two-sample t-test will be conducted to compare the tobacco>rose and strawberry vanilla>rose odor difference score z-statistic image separately for each 18 mg/ml ECIG flavor group. These t-tests will identify anatomical regions with significant effects of nicotine level and assigned vs. unassigned flavor over time. We expect that BOLD activity in regions implicated in smoking cue-reactivity will increase more over the conditioning phase for the 18 mg nicotine group compared to the 0mg nicotine group and for odors from the assigned vs. unassigned flavor.

Aim 3: Determine if strawberry vanilla results in stronger cue-reactivity than tobacco flavor. A two-sample t-test will be conducted for the assigned flavor (strawberry vanilla or tobacco) > control rose difference score z- statistic images comparing the flavor groups. These t-tests will identify anatomical regions with significant flavor group (tobacco vs. strawberry vanilla) by time (baseline to post-randomization) interaction effects on each odor image. For this analysis, only the 18 mg/ml nicotine content flavor groups will be included.

Exploratory Behavioral Aim: Determine if changes in flavor cue-reactivity are associated with changes in ECIG satisfaction, liking, craving, and dependence. One-sample t-tests will assess for anatomical regions where BOLD changes in odor cue-reactivity are correlated with changes in behavioral measures of e- cig satisfaction, craving, and dependence collected at the 2-week check-in and post-randomization visit, and changes in ECIG liking collected at the baseline and post-randomization visits.

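### Visits 3 and 4 share Day 21 with no minimum gap, so the check-in-to-end behavioral changes in the exploratory aim can span 0 to 28 days, and the analysis does not adjust for it

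*Combined protocol and SAP*

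**What the plan says.** Section 7.2.4 is headed "Conditioning Phase Check-in Visit (Day 14 ± 7 days" and section 7.2.5 "Post-Conditioning fMRI Visit (Day 28 ± 7 days". Both windows count from Day 0. Neither section, nor the missed-window rule in section 3.3.1, sets a minimum time between the two visits.

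In section 8.3, the Exploratory Behavioral Aim relates BOLD change to changes in e-cig satisfaction, craving and "dependence collected at the 2-week check-in and post-randomization visit". No term for elapsed time is mentioned. ECIG liking is treated differently: the aim uses "changes in ECIG liking collected at the baseline and post-randomization visits".

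Table 1 lists ECIG dependence and the ECIG evaluation scale (which I take to be the source of the satisfaction score) at Visits 3 and 4 only. Craving is also listed at Visit 2.

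Three other statements bear on the timing:

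- Section 7.3 says that Visits 2, 3 and 4 "will happen within a 4 week period", and that participation lasts 5 to 8 weeks.
- Section 7.2.5 allows part of Visit 4 to be done by video: "The remote assessments will be conducted via a Zoom session ± 3 days of the scheduled in-Person MRI".
- At the end of Visit 3, participants are told to "remain abstinent from all tobacco products including their ECIG for 14 hours prior to the next study visit".

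**The concern.** A change score has a common meaning across participants only if it covers roughly the same time. Here one participant's change in dependence may cover a few days and another's four weeks, and section 8.3 would treat the two as equivalent. If dependence or satisfaction moves during conditioning, part of the spread in the change scores reflects booking dates rather than differences between people. That spread is noise in a correlation with BOLD change, in a trial of 56 randomized participants.

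For ECIG dependence and the ECIG evaluation scale there is no earlier measurement to fall back on, so Visit 3 is the only reference point. The protocol also disagrees with itself about how late Visit 4 may be, so the possible range of the interval cannot be settled from the text.

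**Working it through.** **Range of the interval** (windows from sections 7.2.4 and 7.2.5)

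1. Nominal, from Table 1: 28 − 14 = 14 days.
2. Shortest: (28 − 7) − (14 + 7) = 21 − 21 = 0 days.
3. Longest: (28 + 7) − (14 − 7) = 35 − 7 = 28 days.
4. If the 4-week span in section 7.3 binds, Visit 4 is no later than Day 28: 21 − 21 = 0 to 28 − 7 = 21 days.
5. If the 5-week minimum also binds and Visit 1 is at Day −7 (Table 1), Visit 4 must fall on Day 28: 28 − 21 = 7 to 28 − 7 = 21 days.
6. If the Visit 4 questionnaires are done in the ± 3-day remote session, case 2 to 3 widens to −3 to 31 days. This is conditional: Table 1 separates remote from in-person items by color, which the text available to me does not show.

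**Illustrative loss of correlation.** Assumptions, none of them in the documents: visits uniform within their windows; change = personal rate × gap; rate independent of gap, with between-person CV *c* of 0.5 to 1.0; scales free of error.

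For gap *g*, the correlation between the observed change and the true rate is

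m = c·E[g] / √((1 + c²)·E[g²] − E[g]²).

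- Full windows: E[g] = 28 − 14 = 14; variance = 14²/12 + 14²/12 = 32.67 (SD 5.7); E[g²] = 196 + 32.67 = 228.67.
- c = 0.5: 7 / √(285.83 − 196) = 7/9.48 = 0.74.
- c = 1.0: 14 / √(457.33 − 196) = 14/16.17 = 0.87.
- Share of gaps under 7 days: 7²/(2 × 14²) = 12.5%; by symmetry 12.5% exceed 21 days.

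Adjusting for *g* removes the average change per day and leaves (rate − mean rate) × g. Its correlation with the rate is E[g]/√E[g²] = 14/√228.67 = 0.93, whatever *c* is.

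**Under the section 7.3 readings**

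- Visit 4 on Days 21 to 28: E[g] = 24.5 − 14 = 10.5; variance = 49/12 + 196/12 = 20.42; E[g²] = 130.67. m = 5.25/√(163.33 − 110.25) = 0.72 and 10.5/√(261.33 − 110.25) = 0.85; adjusted, 10.5/√130.67 = 0.92.
- Visit 4 on Day 28: E[g] = 14; variance = 196/12 = 16.33; E[g²] = 212.33. m = 7/√(265.42 − 196) = 0.84 and 14/√(424.67 − 196) = 0.93; adjusted, 14/√212.33 = 0.96.

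**Covariate plus a 7-day minimum gap**, keeping the full windows and dropping gaps under 7 days. Below 14 days the density of *g* is g/196. The removed part contributes 343/588 = 0.583 to E[g] and 2401/784 = 3.06 to E[g²]. So E[g] = (14 − 0.583)/0.875 = 15.33, E[g²] = (228.67 − 3.06)/0.875 = 257.8, and the adjusted value is 15.33/√257.8 = 0.95.

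**Bookings under 14 hours apart.** With uniform timing, (14/24)²/(2 × 14²) = 0.340/392 = 0.09%, or 56 × 0.0009 = about 0.05 participants. Counted in whole days, 1 of the 15 × 15 = 225 allowed day pairs is same-day and 3 are at most one day apart.

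**The case against.** The best defense is that the reach is small and the size is assumed. Only one exploratory analysis uses the Visit 3 interval, most bookings will fall away from the window edges, and every multiplier rests on a model that the documents do not supply. Linear accrual is doubtful for established daily e-cigarette users, whom section 3.1 admits. If the average change is near zero (large *c*), the unadjusted multiplier is already close to 0.93 and the covariate gains almost nothing. With noisy questionnaires the interval matters less. If reliability of change is 0.5 (assumed), error variance c²·196 is added under the root; relative to a fixed 14-day gap the loss is (7/√138.83)/√0.5 = 0.84 to (14/√457.33)/√0.5 = 0.93. Also, the BOLD change itself covers 21 to 35 days, so the rate of behavioral change is not exactly the quantity being correlated. All of this stands, and it limits the point to a minor one. It does not remove the unequal interval or the conflict with section 7.3.

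A reader might infer more: that the late abstinence instruction endangers the second scan and so the primary endpoint. The documents do not support this. The instruction fails only when fewer than 14 hours separate the visits. A check-in ending at 17:00 and a scan at 09:00 the next day are 16 hours apart. Participants received the same instruction before the first scan (section 7.2.2), and a reminder call is planned about two days before each visit (section 7.2.7); its script is an attachment that is not shown, so it cannot be said to omit abstinence. Nor does the check-in generally lose its purpose of solving barriers to use. That applies only to check-ins close to Day 21, and daily diaries run throughout.

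**Conclusion.** The point holds as a minor design and analysis improvement. The Visit 3 to Visit 4 interval can be 0 to 28 days by the windows, or 0 to 21 or 7 to 21 days under the two readings of section 7.3, and nothing in section 8.3 accounts for it. Only the satisfaction, craving and dependence correlations in the Exploratory Behavioral Aim are materially affected. Aims 1 to 3 use the scans at Visits 2 and 4, and ECIG liking runs from baseline.

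The range follows from the documents alone. The multipliers (0.74 to 0.87 unadjusted, about 0.93 adjusted) are illustrations that depend on uniform timing, linear accrual, the assumed CV and error-free scales. Too little time for the 14-hour abstinence is an edge case of about 0.1% under uniform timing.

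**What to change.** 1. Reconcile sections 7.2.4, 7.2.5 and 7.3, so that the visit windows, the 4-week span and the 5-week minimum agree.
2. State a minimum interval between Visit 3 and Visit 4, for example 7 days. This also removes the edge case of visits less than 14 hours apart.
3. In section 8.3, include the actual number of days from Visit 3 to Visit 4 as a covariate in the exploratory correlations that use the Visit 3 to Visit 4 change.

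Do not divide the change by days. That inflates measurement error when the gap is short, and it pairs a behavioral rate with a BOLD change left as a total. Narrowing the Visit 3 window to ± 3 days is also less attractive, because more participants would then miss a window and come under the withdrawal provision in section 3.3.1.

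The cost is a few words in section 7, one line in section 8.3, slightly less freedom in booking, and one degree of freedom per model.

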7.2.5 Post-Conditioning fMRI Visit (Day 28 ± 7 days) – In Person/Remote

Participants will attend a final visit to complete biomeasures, computerized surveys, the adverse events assessment, and the same fMRI tasks as the baseline MRI visit as indicated in Table 1. Some of the measures can be done remotely via Zoom, others will need to be completed in person. The remote assessments will be conducted via a Zoom session ± 3 days of the scheduled in-Person MRI. This is being done to limit the amount of face-to-face time during study visits. eCO will be measured and urine will be collected for cotinine and pregnancy tests. At the end of the visit, participants will be debriefed and counseled on smoking cessation. All participants will be given a copy of the Surgeon General's booklet 'How Tobacco Smoke Causes Disease' (SEE ATTACHMENT: Surgeon General's Booklet).

Table 1: Measures Table (Black X – In Person; Green X – Remote)

	Final Screening	Randomization/ Pre-Conditioning fMRI	Check-In	Post- Randomization fMRI
Visit	1	2	3	4
Day	-7	0	14	28
QUESTIONNAIRES				
Visit Screener	X			
Tobacco Use History	X			
Name Registry	X			
MRI Safety Form	X	X		X
Demographics	X			
Medical History	X			
Concomitant Medications	X	X	X	X
Adverse Event Assessment		X	X	X
Cigarette Details	X			
CCQ (Clinical COPD Questionnaire)	X	X	X	x
Alcohol Audit-C	X			
NIDA Quick Screen	X			
Environmental Smoke Questionnaire	X			
MINI Psychiatric Interview	X			
Daily Smoking and ECIG Use Logs	X (cigarette only)	X	X	X
Cigarette Dependence (Fagerstrom and Penn State Cigarette Dependence Index)		X	X	X
Minnesota Withdrawal Scale		X	X	X
Craving		X	X	X
Cigarette liking scale		X	X	X
ECIG Use History	X	X	X	X
ECIG evaluation scale			X	X
ECIG Side Effects			X	X
ECIG dependence			X	X
ECIG Perceived Health Risk			X	X
ECIP Patterns of Use			X	X
Perceived Benefits and Harms of Using ECIG		X		X
PROCEDURES				
B-SIT Smell Test		X		
fMRI Cue-Reactivity Task in Scanner		X		X
BIOMEASURES				
Pregnancy Test		X		X
Exhaled CO		X		X
Urine Sample Collection		X		X
NICCHECK Rapid Cotinine Test		X		X

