1.3 Secondary Study Endpoints

The secondary study endpoints are cigarette dependence, ECIG dependence, ECIG liking and satisfaction, and flavor liking.

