3.0 Inclusion and Exclusion Criteria

3.1 Inclusion Criteria

1. Aged 21-60
2. Smoke filtered cigarettes/machine-rolled cigarettes (≥ 5 cigarettes per day) or daily e-cigarette use for past year
3. No serious quit attempt in prior month. This includes use of any FDA approved smoking cessation medication (varenicline, bupropion [used specifically as a quitting aid], patch, gum, lozenge, inhaler, and nasal spray) in the past 1 month as an indication of treatment seeking.
4. Willing to supplement cigarette smoking with ECIG use for 4 weeks or replace e-cigarette with study product for 4 weeks
5. Willing to attend regular visits over a 4-week period (not planning to move, not planning extended vacation, no planned surgeries)

6. Willing to undergo two fMRI scans
7. Able to read and write in English
8. Able to understand and consent to study procedures
9. Access to computer with internet service that allows for use of Zoom

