7.2.8 Daily Dairies for ECIG and Cigarette Use

Prior to randomization, participants will be asked to track the number of cigarettes smoked per day using a paper daily diary. They will also receive a daily REDCap survey link via text message (through Twilio) to enter their cigarette usage. During the 4-week ECIG conditioning period, participants will be required to record their ECIG use (in puffs per day) and the number of cigarettes smoked. A paper-based daily diary designed for data collection of each product type will be used. Participants will also continue reporting their use via REDCap survey links each evening. Research assistants will review the data entered by participants via the REDCap survey links at each visit. If participants did not complete the survey online, the researcher will ask the participant at each visit their ECIG and cigarette use. The diary will be used as a memory aid for the participant. (SEE ATTACHMENT: Cigarette Pack Daily Diary and E-cigarette and Cig Daily Diary)

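### ECIG dependence, a secondary endpoint, is first measured at Day 14 although daily e-cigarette users are eligible, so its change from baseline cannot be estimated or adjusted for

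*Combined protocol and SAP*

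**What the plan says.** Section 1.3 lists the secondary endpoints as "cigarette dependence, ECIG dependence, ECIG liking and satisfaction, and flavor liking". Inclusion criterion 2 in Section 3.1 accepts either smokers of at least five cigarettes a day or people with "daily e-cigarette use for past year". Under criterion 4 the latter must be willing to "replace e-cigarette with study product for 4 weeks".

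Table 1 in Section 7.2.5 sets the measurement times:

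- The row "ECIG dependence" is marked at Visit 3 (Day 14) and Visit 4 (Day 28) only.
- Cigarette dependence is marked at Visits 2, 3 and 4.
- The row "ECIG Use History" is marked at all four visits, including screening and Day 0.
- The daily use log is restricted to cigarettes at Visit 1.

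The text agrees with the table. Section 7.2.3 names cigarette dependence among the baseline questionnaires and does not name ECIG dependence. Section 7.2.8 states: "Prior to randomization, participants will be asked to track the number of cigarettes smoked per day using a paper daily diary". ECIG puffs enter the diary only in the four-week conditioning period.

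Section 8.3 (exploratory behavioral aim) takes change in dependence from the two-week check-in to the final visit. The same section defines the BOLD change image as post-conditioning minus baseline. Section 7.4.3 stratifies randomization by gender with matching on age; user type is not a stratum.

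**The concern.** The schedule suits smokers who are new to e-cigarettes: they have no ECIG dependence to record at Day 0. It does not suit the second eligible group. Someone who has vaped daily for a year arrives with some level of dependence on their own product, and a Day 14 or Day 28 score carries that level together with anything the study product adds. With no earlier score on the same scale, the two parts cannot be split within a person.

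Three things are at stake:

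- Change from baseline in a named secondary endpoint cannot be computed.
- The Visit 4 comparison between arms cannot be adjusted for the endpoint's own baseline, which is usually the most useful covariate.
- The exploratory correlation sets a brain change over the whole conditioning period against a dependence change over its second half, so any dependence that develops in the first two weeks is lost.

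**Working it through.** The plan gives no sample size, power or alpha for ECIG dependence, so there is no figure of its own to reproduce. The check is a reading of the schedule followed by two illustrations on assumed inputs.

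**Step 1. Schedule (Table 1).** Two visits precede use of the study product: Visit 1 and Visit 2, where it is dispensed at the end.

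| Item | Marked at Visits 1–2 | Marked at Visits 3–4 |
|---|---|---|
| ECIG dependence | 0 of 2 | 2 of 2 |
| Cigarette dependence | 1 of 2 (Visit 2) | 2 of 2 |
| ECIG Use History | 2 of 2 | 2 of 2 |

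Section 8.3 independently places the first dependence score at the two-week check-in, so the empty cells in Table 1 are not an artefact of text extraction.

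**Step 2. Periods in the exploratory aim (Section 8.3).** The BOLD change runs from Day 0 to Day 28, nominally 28 days. The dependence change runs from Day 14 to Day 28, nominally 14 days. Each of these two visits has a window of ±7 days (Sections 7.2.4 and 7.2.5). Taking the windows alone, the dependence interval could run from 21 − 21 = 0 days to 35 − 7 = 28 days.

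**Step 3. Chance imbalance in user type.** Inputs: 56 randomized 1:1:1:1 (Section 7.4.3), so 56/4 = 14 per arm, with no user-type stratum. The documents do not give the share p of vapers; 10%, 25% and 50% are assumptions. Treat the vaper counts in two arms, X and Y, as independent Binomial(14, p). A difference of four is 4/14 = 29 percentage points.

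| Assumed share p | P(\|X − Y\| ≥ 4) |
|---|---|
| 10% | 0.028, about 3% |
| 25% | 0.124, about 12% |
| 50% | 0.185 (0.1849), about 18% |

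For p = 0.5 this can be checked directly: X − Y + 14 is Binomial(28, 0.5), and 2 × P(Binomial(28, 0.5) ≤ 10) = 0.1849.

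**Step 4. Precision.** If the baseline and Visit 4 scores correlate r among vapers, adjusting for baseline multiplies their residual variance by 1 − r². The documents give no r; these values are assumptions.

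| Assumed r | 1 − r² | Variance removed |
|---|---|---|
| 0.3 | 0.91 | 9% |
| 0.5 | 0.75 | 25% |
| 0.7 | 0.51 | 49% |
| 0.8 | 0.36 | 64% |

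This gain applies to vapers only. Among smokers who do not vape the baseline score would be constant, so it explains nothing beyond user type.

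**The case against.** A reader might infer from the cigarette-only log that ECIG use before randomization is not recorded at all. The documents contradict that. ECIG Use History is scheduled at Visits 1 and 2, Tobacco Use History at Visit 1, and past-year daily use has to be established for eligibility. What is missing is a prospective daily ECIG count and a dependence score. The contents of ECIG Use History are not given, so whether it includes any dependence items is unknown.

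A reader might also infer that prior dependence cannot be separated from a study effect in any analysis. That goes too far. Assignment is randomized, so prior dependence does not bias a between-arm comparison of Visit 4 scores in expectation. The statement holds only for within-person change and for attributing a level of dependence to the study product.

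It can further be said that user type is already known and could be a covariate with no new measurement, so the imbalance figures in Step 3 argue for adjusting by user type and not, by themselves, for a baseline scale. This stands. What the scale adds is the degree of dependence among vapers, which user type does not capture. Section 8.3 specifies neither adjustment.

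Finally, the stakes are limited. The study is a proof of concept and Section 8.2 looks for trends. Section 8.3 names no between-arm test of ECIG dependence, only the exploratory correlation, and the primary fMRI endpoint has a baseline scan. Sections 7.4.4 and 15.6 are written with smokers in mind, so the vaper share may be small. All of this lowers the weight of the point. None of it supplies a baseline for an endpoint that Section 1.3 names.

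**Conclusion.** The point holds as a gap in the measurement schedule of a secondary endpoint. For past-year daily e-cigarette users, change from baseline in ECIG dependence cannot be estimated, Visit 4 scores cannot be baseline-adjusted, and the exploratory aim compares changes over different periods. These conclusions rest on the documents alone.

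The sizes rest on assumptions. The chance of a difference of four or more vapers between two arms lies between about 3% and 18% for shares of 10% to 50%, and the variance removed among vapers lies between 25% and 49% for correlations of 0.5 to 0.7. Between-arm comparisons are less precise than they could be but not biased in expectation, and the primary endpoint is untouched. The change is worth making because it is cheap and because a baseline cannot be recovered once the study product has been dispensed.

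**What to change.** 1. Give the existing ECIG dependence scale at Visit 1, or at Visit 2 before the study product is dispensed. It should not go into the remote session that Section 7.2.3 allows within three days after the scan, because by then the participant has the device. Define in advance the score for people who do not vape.
2. Record ECIG use as well as cigarettes in the pre-randomization log and diary (Table 1, Section 7.2.8).
3. In Section 8.3, state that Visit 4 ECIG dependence will be analysed with adjustment for the baseline score and user type.
4. In the exploratory aim, use the baseline to Visit 4 change in dependence, so that it covers the same period as the BOLD difference.

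The cost is a few extra minutes of a questionnaire already in use and one additional log column. No new visit, instrument or staff is needed. For participants already dispensed the product, the baseline is lost; user type and ECIG Use History remain available as covariates.
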